8.3 Sample Size and Power Determination

Phase 1: It is expected that a sample size of 15 subjects will adequately determine if there is a significant intolerance of the tested doses of ALA in the elderly population.

Phase 2: In addition to assessing the safety profile of ALA and the feasibility of study procedures, one of the major goals of the proposed study is to determine if additional, larger scale assessments of efficacy are warranted. For pilot studies, it is appropriate to use a confidence interval approach to evaluate outcomes and pre-specify a clinically important threshold to determine if further investigation is justified.⁵⁰⁻⁵¹ If we decide to halt investigation if the observed growth rate in the actively treated group is greater than in the placebo group, then it is reasonable to use a one-sided confidence interval. With 50 total subjects, we can be 90% confident (one-sided) that the “effect size” of ALA in reducing the GA growth rate is 0.4 or less. This number assumes that 15% of subjects dropout. An example of an effect size of 0.4 would be a growth rate of 0.40 mm in the placebo group and a growth rate of 0.32 (20% reduction) in the ALA group when the standard deviation of the annual growth rate is 0.20 mm.⁵² Interventions with less efficacy than this may not be worth pursuing.

Based on current data, it is possible that approximately 25% of subjects randomized to the ALA arm may not tolerate 1200 mg of ALA. Instead of 1200 mg once daily of ALA, some of these patients may elect to take 600 mg twice daily or 600 mg once daily. An intention to treat analysis will be performed on all subjects randomized to 1200 mg ALA in comparison to the placebo group. Subgroup analyses will be performed on those subjects remaining at 1200 mg and subjects at a lower dose of ALA. After 25 subjects have enrolled in the study, we will perform interim analyses of the numbers of subjects in these subgroups without evaluating any outcomes data. Depending on the status of enrollment, drop-out rates, and the size of the subgroup consistently taking 1200 mg subgroup, the study sample size may be increased at this time so that the 1200 mg subgroup has a number equal to or nearly equal to 22 subjects available for analyses.

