8.4 Statistical Methods

Phase 1: Percentages of adverse events will be calculated.

Phase 2: As a preliminary analysis, the mean change in the total area of GA within study eyes over 18 months (from the time of randomization) will be compared between eyes receiving the active ALA dose and placebo supplementation; a square root transformation will be applied to the area measurements to mitigate the dependence of growth rate on initial size.⁵³⁻⁵⁴ Also, mean change in visual acuity over 18 months, the proportion with a decrease of 15 letters (3 lines) of visual acuity, and the proportions with serious adverse events will also be compared. Variants of the independent t-test and chi-square tests of proportions that account for the correlation between eyes of subjects who have two study eyes will be used to make comparisons.

The main analysis for comparing treatment groups will compare the rates of change in total area of GA using a mixed effects linear model. Use of this model allows including all patients in the analysis and requires less stringent assumptions than a complete cases analysis regarding the association of

CONFIDENTIAL

missingness with the outcome variable and does not introduce bias into the estimation of the slope parameter as a “last observation carried forward (LOCF)” approach does when area changes with time. Both subject and eye will be considered random effects. A sensitivity analysis using multiple imputation for missing values will be used for the analysis of mean change between baseline and 18 months and for the mixed effects linear model of total area.

Similar analytic methods using mixed effects models will be used for the other outcome measures.

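### Section 8.4's main model of GA growth rates names no random slope on time; fitted with random intercepts only, its confidence limit would be too tight

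*Combined protocol and SAP*

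**What the plan says.** On the main analysis, section 8.4 of the combined protocol and SAP states: "The main analysis for comparing treatment groups will compare the rates of change in total area of GA using a mixed effects linear model". The random part is described only by "Both subject and eye will be considered random effects". The section also argues that the model "does not introduce bias into the estimation of the slope parameter". No section says whether intercepts, slopes or both vary, and none gives a within-eye covariance structure, a robust variance or a degrees-of-freedom method. For the preliminary comparisons, section 8.4 does plan "Variants of the independent t-test and chi-square tests of proportions that account for the correlation between eyes of subjects who have two study eyes".

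Four other points in the document bear on this:

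- Section 7.2.1 sets imaging at baseline, 6, 12 and 18 months only.
- Section 4.2.1 allows both eyes of a subject to be enrolled.
- Section 8.3 says that "it is appropriate to use a confidence interval approach to evaluate outcomes and pre-specify a clinically important threshold". It describes a one-sided 90% limit at an effect size of 0.4 with 50 subjects and 15% dropout.
- Its worked example has a placebo growth rate of 0.40 mm and an ALA growth rate of 0.32 mm, where "the standard deviation of the annual growth rate is 0.20 mm".

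**The concern.** The treatment effect is a difference in slopes, so its standard error depends on how the model treats variation in slope. A random-intercept model lets eyes start at different lesion sizes but gives every eye in an arm the same growth rate. An eye that truly grows faster or slower than its arm's mean then appears as independent noise at each visit. Most of that variation drops out of the SE. If both eyes of a subject are enrolled, the correlation between their slopes is ignored as well.

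At stake is the pilot's main output, the limit on how large the ALA effect could be. Section 8.3 sizes that limit on the SD of growth rates between subjects. An analyst could follow section 8.4 as written and report a narrower limit than the trial was sized to give. The bound on the ALA effect would then look firmer than the data support.

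**Working it through.** **Inputs from the documents.** Visits at t = 0, 0.5, 1.0 and 1.5 years (7.2.1); 50 subjects, 15% dropout, one-sided 90% confidence, effect size 0.4 and growth-rate SD 0.20 mm (8.3); 1:1 allocation (3.1).

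**Assumed, because the documents do not give them.** The residual SD s at a visit, hence rho; the share p of subjects with two study eyes; the correlation r of true slopes between a subject's eyes.

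**1. The plan's own figure.** For a one-sided 90% half-width of 0.4 SD, n per arm = 2*(1.2816/0.4)^2 = 20.5, rounded up to 21. That is 42 in total, and 42/0.85 = 49.4, or 50 subjects. With 50*0.85/2 = 21.25 per arm, the half-width is 1.2816*sqrt(2/21.25) = 0.393 SD, or 0.400 with a t quantile. The stated 0.4 is reproduced. The SE behind it is 0.20*sqrt(2/21.25) = 0.0614 mm per year.

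**2. Formula for one eye per subject.** Deviations of t from 0.75 are -0.75, -0.25, 0.25 and 0.75, so Sxx = 0.5625 + 0.0625 + 0.0625 + 0.5625 = 1.25. Let tau^2 be the true slope variance.

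- Variance of a fitted per-eye slope: V = tau^2 + s^2/1.25.
- In an intercept-only fit each eye contributes 3 within-eye degrees of freedom. The residual variance estimates (1.25*tau^2 + 3*s^2)/3, and dividing by Sxx gives tau^2/3 + s^2/1.25.
- With rho = tau^2/V, the second quantity is V*(1 - 2*rho/3).
- True SE / model SE = 1/sqrt(1 - 2*rho/3).

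**3. Numbers, reading 0.20 mm as the SD of observed slopes (V = 0.04).** Here rho = 1 - (s^2/1.25)/0.04 and coverage = Phi(1.2816/factor).

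| Assumed s (mm) | rho | Factor | Model SE (mm/yr) | Reported half-width (SD) | Actual coverage of 90% limit |
|---|---|---|---|---|---|
| 0.05 | 0.95 | 1.65 | 0.0372 | 0.238 | 78% |
| 0.10 | 0.80 | 1.46 | 0.0419 | 0.269 | 81% |
| 0.15 | 0.55 | 1.26 | 0.0488 | 0.313 | 85% |
| 0.20 | 0.20 | 1.07 | 0.0571 | 0.366 | 88% |

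If 0.20 mm is instead the SD of true slopes, the factors are 1.66, 1.50, 1.36 and 1.26, with coverage 78%, 80%, 83% and 85%.

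**4. Two-eye subjects.** Factor^2 = (1 + p + 2*p*r*rho)/((1 + p)*(1 - 2*rho/3)). Example with p = 0.25, r = 0.7, s = 0.05 mm: (1.25 + 0.3325)/(1.25*0.3667) = 3.45, so the factor is 1.86. With r = 0.7 and p from 0.25 to 0.5, the factor is 1.35 to 1.98 for s of 0.05 to 0.15 mm, and 1.10 to 1.12 at 0.20 mm.

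**5. Simulation checks.**

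- In 20,000 balanced trials per setting with 21 per arm, the ratios at rho = 0, 0.5 and 0.8 were 0.997, 1.228 and 1.464. The formula gives 1.000, 1.225 and 1.464.
- REML fits with 15% dropout and visits moved by up to 3 months gave 0.95, 1.21 and 1.46 (600 trials each, Monte Carlo error about 3%).
- With 25% two-eye subjects, r = 0.7 and 15% random dropout (500 trials per setting, s = 0.05 / 0.10 / 0.15 / 0.20 mm), the intercept-only fit covered 74 / 78 / 83 / 87%. A model with random slopes for subject and for eye covered 88 / 90 / 91 / 90%. Monte Carlo error is about 1.3 points near 90%.

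**The case against.** The strongest reply is that section 8.4 is underspecified, not wrong. It is as silent about intercepts as about slopes. It speaks of rates of change and of a slope parameter, and it attends to between-eye correlation in the preliminary tests. Section 8.3 counts variation in growth rate between subjects. The authors may well have meant random slopes. This stands: the documents do not show that an intercept-only model is intended. It does not remove the problem, because random intercepts are the ordinary coding of the sentence and nothing elsewhere corrects it.

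The second reply is that little hangs on the interval. Section 8.3 is itself conditional ("If we decide to halt investigation if the observed growth rate in the actively treated group is greater than in the placebo group"). It does not say which analysis supplies the one-sided limit, and it writes no rule on that limit's value. The halt condition compares observed growth rates and uses no SE. The preliminary comparison of 18-month change does not have this defect. All of this stands, and it limits the consequence to the reported precision of the main analysis.

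A third reply is that the size is assumed throughout. This also stands: rho could be near 0, where the factor is 1.0.

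A reader might also infer that the other outcomes share the defect, because "Similar analytic methods using mixed effects models will be used for the other outcome measures". The documents do not support that. The methods are called similar, not identical; several of those outcomes are changes and not slopes; and no calculation was made for them.

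**Conclusion.** The point holds in conditional form. If section 8.4 is fitted with random intercepts for subject and eye, the SE of the slope difference is too small for any rho above 0, and the error always makes the interval too narrow. For one eye per subject and residual SDs of 0.05 to 0.20 mm, the understatement is about 1.65-fold down to 1.07-fold, and a nominal 90% one-sided limit covers about 78% to 88%. Two-eye subjects with positively correlated slopes increase it.

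The algebra is certain for four balanced visits and barely changes with dropout and the visit window. It depends only on rho, so it applies with or without the square-root transformation; the residual SDs above are on the mm scale of section 8.3. The value of rho and the model that would actually be fitted are not known from the documents.

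A reader might quote 1.73, the value of the formula at rho = 1. That requires areas measured without error, which is not realistic for the grader-operated semi-automated measurement in section 7.2.3, so it should not be used as the size of the problem. Nor do the documents support saying that the sample size or the halt condition is wrong: the 0.4 bound reproduces, and the halt condition uses no SE.

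**What to change.** In section 8.4, state that the main model has fixed effects for arm, time and arm by time, with random intercepts and correlated random slopes on time for subject and a random intercept for eye within subject. Add an eye-level slope only if it can be estimated. Name one fallback for non-convergence or a boundary fit: the same fixed effects with subject-clustered, small-sample-corrected SEs. State in 8.3 or 8.4 that the one-sided 90% limit comes from this model.

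The cost is wording only, with no added subjects or visits. The interval will be wider than under an intercept-only fit but close to what section 8.3 already claims. In the simulation with 25% two-eye subjects, half-widths in SD units were 0.21 to 0.32 for the intercept-only fit, 0.37 for random slopes at both levels, and 0.36 to 0.39 for the intercept-only fit with subject-clustered SEs. The plan's own figure is 0.39 to 0.40.

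Some limits remain. The simulated random-slope model had slopes for both subject and eye; the version with a subject slope and eye intercept was not simulated separately. The optimizer reported convergence in all 2,500 of those fits, but near-zero variance estimates were not counted. With about 42 completers and possibly few two-eye subjects, boundary fits are plausible, which is why the fallback should be fixed in advance.

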8.4.1 Baseline Data

Baseline and demographic characteristics will be summarized by standard descriptive statistics (including mean and standard deviation for continuous variables such as age and standard percentages for categorical variables such as gender).

8.4.2 Safety Analysis

Phase 1: All subjects entered into the study will have detailed information collected on adverse events for the overall study safety analysis. Symptoms reported will be graded as mild, moderate, or severe in nature.

Phase 2: All subjects entered into the study and randomized at the baseline visit will have detailed information collected on adverse events for the overall study safety analysis

9 Safety and Adverse Events

9.1 Definitions

9.1.1 Adverse Event

An **adverse event** (AE) is any untoward medical occurrence associated with the use of a drug in humans, whether or not considered drug related. Abnormal results of diagnostic procedures are considered to be adverse events if the abnormality:

- results in study withdrawal
- is associated with a serious adverse event
- is associated with new clinical signs or symptoms
- leads to additional treatment or to further diagnostic tests
- is considered by the investigator to be of clinical significance

9.1.2 Serious Adverse Event

Serious Adverse Event

Adverse events are classified as serious or non-serious. A **serious adverse event** is any AE that results in any of the following outcomes:

- Death
- A life-threatening adverse event
- Inpatient hospitalization or prolongation of existing hospitalization
- A persistent or significant incapacity or substantial disruption of the ability to conduct normal life functions. Example, loss of 6 lines of visual acuity on the ETDRS chart
- A congenital anomaly or birth defect

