1.2.2 Clinical Data to Date

ALA has been approved for the treatment of diabetic peripheral neuropathy for many years in Germany.⁵⁻⁸ It also has been studied in clinical trials for a variety of diseases including cardiovascular disease, diabetes, schizophrenia, and others.³⁴ It is commonly used at doses of 200-600 mg and is already available over-the-counter.

The safety of ALA has been extensively evaluated. ALA is metabolized by the liver and is known to be safe in both hepatic and renal disease. The primary side effects from oral ALA are gastrointestinal and occur at doses of 1200 mg or higher. These gastrointestinal side effects predominantly involve an upset stomach, gastric reflux, nausea, and can be minimized if ALA is taken in divided doses or with a meal, although concurrent food ingestion may partially reduce the bioavailability.³⁵⁻³⁷ There can also be a malodorous urine and headache. Rare complications that may be related to ALA include one subject that developed an allergic rash, fever, and mild thrombocytopenia that resolved after stopping ALA and reports of a rare occurrence of insulin autoimmune syndrome.³⁸⁻³⁹ Insulin autoimmune syndrome is treatable and resolves within a few months after cessation of ALA. Most of these published studies on the safety and tolerability of ALA at doses of 1200 mg or higher involve adults that are not elderly.

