7.4 Unscheduled Visits

Unscheduled visits will be handled as typical standard of care visits by the treating ophthalmologist. Any exams and tests at unscheduled visits will be billed to the subject's insurance per the usual practices of that ophthalmologist. At the next scheduled study visit, any adverse events related to the need for the unscheduled visits will be recorded. If there is a significant change in exam or a new diagnosis noted at the time of the unscheduled visit (i.e. new choroidal neovascularization, retinal vein or artery occlusion, vitreous hemorrhage, etc.), the Sponsor will be notified

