9.4 Reporting of Adverse Events and Unanticipated Problems

The Data Coordinating Center receives notification of Serious Adverse Events (SAEs) via a specific form completed by the investigator and submitted within 24 hours. An assessment of all incoming SAEs is made to determine whether the event needs to be reported to the FDA. The Coordinating Center sends an electronic copy of each Serious Adverse Event Report Form, as well as baseline medical history, medications reported at baseline and follow-up, and other supporting documentation as needed to the Sponsor within 24 hours. The Coordinating Center also sends all AEs to the Sponsor. All SAEs are reviewed by the Sponsor as required by regulation.

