9.4.1 Investigator reporting: notifying the study sponsor

Any serious adverse event will be reported to the study Sponsor within 24 hours of the event. To report such events, a Serious Adverse Event (SAE) form will be completed by the Investigator and sent to the Sponsor, via the Data Coordinating Center, within 24 hours. The Investigator will keep a copy of each SAE form on file at the study site. Report serious adverse events to:

Clinical Trials Coordinating Center
Center for Preventive Ophthalmology and Biostatistics
[name]
[name]
[contact]
[contact] (fax)

Within the following 24 hours, the Investigator will provide further information on the serious adverse event in the form of a written narrative. This should include a copy of the completed Serious Adverse Event form and any other information that will assist the understanding of the event. Significant new information for ongoing serious adverse events should be provided promptly to the study sponsor.

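### The serious adverse event definition has no criterion for an important medical event needing intervention to prevent a listed outcome, so an event that treatment averts in time is non-serious

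*Combined protocol and SAP*

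**What the plan says.** Section 9.1.2 sorts every adverse event into serious or non-serious. A serious one "is any AE that results in any of the following outcomes", followed by five bullets. The admission bullet reads "Inpatient hospitalization or prolongation of existing hospitalization". The incapacity bullet also covers substantial disruption of normal life functions and carries the only ocular illustration: "Example, loss of 6 lines of visual acuity on the ETDRS chart". The list has no open-ended wording and no criterion based on medical judgment.

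Several provisions turn on that label:

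- Section 9.4.1: "Any serious adverse event will be reported to the study Sponsor within 24 hours of the event".
- Section 9.4: "An assessment of all incoming SAEs is made to determine whether the event needs to be reported to the FDA".
- Section 9.4.4: the Sponsor shares SAEs with participating investigators.
- Section 17.1: the 15-day FDA report requires an event to be drug-associated, unexpected and serious.
- Study Summary, Safety Evaluations: the Phase 1 primary safety outcome is the percentage of subjects with an SAE on alpha lipoic acid (ALA).
- Section 8.4, for Phase 2: "the proportions with serious adverse events will also be compared".

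Elsewhere the protocol names events that matter clinically. Section 7.4 requires the Sponsor to be told of a significant finding at an unscheduled visit, such as "new choroidal neovascularization, retinal vein or artery occlusion, vitreous hemorrhage". Section 1.2.2 mentions "reports of a rare occurrence of insulin autoimmune syndrome" among possible ALA complications.

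**The concern.** The five bullets describe outcomes that have occurred. They leave out an event that would have led to one of those outcomes had it not been treated. CNV shows the problem. Section 1.1 says it can cause acute, severe vision loss. Section 4.2.2 says a subject who develops it in the study eye receives standard intravitreal injections and stays in the trial. If the injection works, no bullet is met.

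The label then decides how quickly the event is seen, whether anyone considers it individually for FDA reporting, whether other investigators hear of it, and whether it enters the one adverse-event proportion that section 8.4 names for comparison between arms. Section 11.1 says there is no Data Safety Monitoring Board, so correct intake of SAEs carries more of the safety oversight.

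**Working it through.** The plan states no figure on this point, so there is none to reproduce. The check is of the text, with one calculation for scale.

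**Step 1. Does any section repair the definition?** Section 9.1.1 defines an adverse event and section 9.2 covers recording; neither touches seriousness. Section 17.1 uses the word serious without redefining it. Sections 6.4 and 7.4 require Sponsor notification of new diagnoses but do not make them serious. Section 9.6.1 refers to a Data and Safety Monitor charter and a safety monitoring plan. They are not in the documents, so any wider definition there cannot be checked.

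**Step 2. Which events fall through?** Outpatient management alone does not make an event non-serious. Significant incapacity or substantial disruption of normal life qualifies without admission, and six lines is an example, not a cut-off. What remains is:

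- an event whose treatment averts all five outcomes, such as CNV injected before major vision loss;
- a new, unlisted drug-related event managed without admission, life threat or significant incapacity.

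A loss of at least three but under six lines counts toward the primary safety endpoint in section 3.2.3. The six-line example does not make it serious, though the investigator could still judge it so under the incapacity bullet.

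**Step 3. What does a non-serious event lose, and what does it keep?** It loses the 24-hour form (9.4, 9.4.1), the case-by-case FDA screen (9.4), sharing with investigators (9.4.4), the Phase 1 primary safety outcome (Study Summary) and the SAE comparison (8.4). It keeps these routes:

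- transfer of all adverse events to the Sponsor, with no deadline (9.4);
- prompt IRB reporting if unexpected and related (9.4.2);
- the FDA Annual Report (9.4.3);
- the Sponsor's aggregate analysis, with no method given (17.1);
- Sponsor notification of new diagnoses, with no deadline and written only for unscheduled visits (6.4, 7.4);
- the three-line acuity comparison (3.2.3, 8.4), if acuity falls that far.

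**Step 4. Which expedited reports are affected?** The 7-day report needs a fatal or life-threatening event, which is already an SAE. Only the 15-day report is exposed, and only for an event that is both drug-associated and unexpected.

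**Step 5. Scale, using CNV.** Inputs: two-year CNV incidence of 2 to 18% in eyes with geographic atrophy (GA) (section 1.1), 18 months of follow-up (4.2.4) and 50 subjects (8.3). Assumptions: constant hazard and one study eye per subject. Section 4.2.1 allows two, which would raise the number of eyes.

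- 18-month risk = 1 − (1 − p)^(18/24)
- p = 0.02: 1 − 0.98^0.75 = 0.0150; × 50 = 0.75, about 0.8
- p = 0.18: 1 − 0.82^0.75 = 0.1383; × 50 = 6.9

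If the 15% dropout assumed in section 8.3 contributed no follow-up, 50 × 0.85 = 42.5 eyes would give 0.6 to 5.9.

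**The case against.** The strongest reply is that the gap is narrow and well cushioned, and much of that stands. A reader might infer four stronger things that the documents do not support.

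- *Every sight-threatening event managed without admission is non-serious.* The incapacity bullet reaches many of them. An acute loss of vision from an artery occlusion or vitreous hemorrhage can qualify. The documents also do not say that occlusion, hemorrhage or insulin autoimmune syndrome is usually managed as an outpatient; only CNV injection implies it.
- *CNV and the known ALA complications would miss expedited FDA reports.* CNV is presented as part of the course of GA and is planned for. Insulin autoimmune syndrome and the case of rash, fever and mild thrombocytopenia are already listed as possible ALA effects. None is clearly unexpected, so calling it serious would not by itself trigger a report.
- *The CNV count measures missed drug signals.* It is background disease. It is also an upper limit, because some cases already qualify as SAEs and others would not meet a judgment-based criterion.
- *Six lines for seriousness conflicts with three lines for the safety endpoint.* One illustrates a reporting category and the other defines an endpoint; they can differ.

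It is also fair that ocular and systemic safety are listed as secondary outcomes (section 8.2), that section 8.4 extends similar methods to other outcome measures, and that section 8.4.2 plans an overall adverse-event analysis. None of these gives a 24-hour report or an individual FDA screen, or puts the event into the SAE proportion. The 15-day route in section 17.1 for an event first judged not reportable does not help either, because the event must still fit criteria that include serious.

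**Conclusion.** The omission is real and nothing in the documents repairs it. An event whose treatment averts death, admission and significant incapacity or disruption is non-serious under section 9.1.2. It loses the fast report, the individual FDA screen, sharing among investigators and a place in the SAE proportions of both phases. The routes that remain are slower, untimed or lead elsewhere.

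The size is modest. On the protocol's own CNV range, at most about 0.8 to 6.9 of 50 study eyes might be reclassified over 18 months, assuming constant hazard and one study eye per subject. Any loss of an expedited FDA report is confined to related, unexpected events, for which the documents give no count. The primary efficacy result is unaffected. The conclusion rests on the protocol's text alone and assumes that the unavailable charter and monitoring plan do not widen the definition. The change is a cheap improvement.

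**What to change.** Add to section 9.1.2: *an important medical event that, in the investigator's judgment, may jeopardize the subject or require medical or surgical intervention to prevent one of the outcomes above.*

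State in sections 6.4 and 7.4 that new diagnoses of the kind named there are assessed against this criterion, whether found at a scheduled or an unscheduled visit, and go on the SAE form if they meet it. Use the same definition for the SAE proportions in section 8.4 and for the Phase 1 safety outcome in the Study Summary. Add a matching line to the SAE form instructions.

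The cost is one bullet, the cross-references, a few more 24-hour forms and slightly higher SAE percentages.
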